## **4. STUDY DESIGN AND RATIONALE**

### **4.1. Description of Study Design**

The study design is controlled, randomized, subject-masked, 3 treatment ×3 period, non-dispensing, contralateral study.

After a pre-screening assessment, eligible subjects will be invited to attend an initial visit. Subjects will be prescreened using the CLDEQ-8 questionnaire with their habitual lenses and those who are classified as symptomatic (CLDEQ-8 score of 20-37) will be scheduled for Visit 1.

At study Visit 1, subjects will be consented and screened for inclusion/exclusion criteria. If a subject is found to meet all eligibility criteria, they will be asked to attend Visit 2 which will take place on a different day. Subjects will be asked to wear their contact lenses early in the morning (at home) on the day of Visit 2 and to rate subjective comfort on a paper VAS scale immediately prior to lens application and 5 minutes post-application. They will be asked to attend the study visit having worn their habitual lenses for  $14 \pm 2$  hours. At Visit 2, one of three areas (upper lid margin, lower lid margin or cornea) will be anesthetized on one eye, whilst the fellow eye will receive a saline placebo treatment in the same location. The ocular surface region and treatment will be randomly assigned. The right eye will always be assessed first. Subjective comfort scores (VAS scale) will be collected prior to and following the treatment on each eye (5 and 10 minutes post-treatment). On the day of corneal treatment, VAS comfort scores will also be collected immediately after lens removal prior to treatment application. Subjects will be asked to return for Visit 3 on a different study day, again having worn their lenses for  $14 \pm 2$  hours and the same procedures as at Visit 2 will take place. The same procedures as for Visit 3 will be repeated for Visit 4. Visits 2-4 will be scheduled 1-14 days apart.

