## **5. TEST ARTICLE ALLOCATION AND MASKING**

### **5.1. Test Article Allocation**

An ocular surface region (upper lid margin, lower lid margin or cornea) will be randomly allocated to each visit and a treatment (anesthesia or placebo) will be randomly allocated to each eye using a randomization scheme supplied by the study biostatistician. A single ocular region will be investigated at each visit and a single treatment will be applied to each eye at each visit. The clinical site will follow the randomization scheme provided and will complete enrollment according to the randomization list and will not pre-select or assign subjects. The assignment of the subjects must be performed at Visit 1. The following must have occurred prior to randomization:

- Informed consent has been obtained
- Subject meets all the inclusion / exclusion criteria
- Subject history and baseline information has been collected

The randomization scheme will be generated using the PROC PLAN procedure from the SAS Software Version 9.4 or higher (SAS Institute, Cary, NC).

The regions (upper lid margin, lower lid margin, or cornea) will be treated in a bilateral and random fashion using a Williams design with 3 regions and 3 periods. Each subject will be randomly assigned to one of six unique sequences (U/L/C, L/C/U, C/U/L, C/L/U, U/C/L, L/U/C). For each region within a sequence, the two treatments will be randomly assigned to the left and right eye (anesthesia left eye/placebo right eye or placebo left eye/anesthesia left eye).

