Visit 2-4 (in clinic after 14 ± 2 hours of lens wear)			
Step	Procedure	Details	
2.4	Adverse Events and Concomitant Medications Review	Review any changes to the subject's medical history or concomitant medications from the previous study visit. Record any changes, and any adverse events.	
2.5	Wearing Time	Record the wearing time since application and comfortable wearing time.	
2.6	Subject Reported Ocular Symptoms	Subjects will respond to a verbal open-ended symptoms questionnaire.	
2.7	Collection of VAS scale	The investigator will collect the comfort VAS scales and will enter the scores on the database.  If subjects have not completed the VAS scales, the visit can be rescheduled to a different day for a maximum of two further occasions.	
2.8	Entrance Visual Acuity	Record the distance high contrast visual acuity to the nearest letter (OD and OS) with their habitual contact lenses.	Eurolens Research SOP #12a
2.9	Slit Lamp Biomicroscopy (white light only)	Efron Slit Lamp Classification Scale will be used to grade the findings.  If any of these slit lamp findings are Grade 3 or higher, it will be recorded as an Adverse Event.	Eurolens Research SOP #13
2.10	Subjective Lens Fit Assessment	Lens fit will be recorded according to a -2 to +2 integer scale for each of the following criteria:  Horizontal centration: -2 = Extremely Nasal -1 = Slightly Nasal 0 = Optimum +1 = Slightly Temporal +2 = Extremely Temporal  Vertical centration: -2 = Extremely Superior -1 = Slightly Superior 0 = Optimum +1 = Slightly Inferior +2 = Extremely Inferior  Coverage: -2 = Extremely Inadequate -1 = Slightly Inadequate 0 = Optimum	

		
+1 = Slightly Excessive +2 = Extremely Excessive
 
Movement -2 = Extremely Inadequate -1 = Slightly Inadequate 0 = Optimum +1 = Slightly Excessive +2 = Extremely Excessive
	
2.11	Subjective comfort	Subjective comfort scores (vertical VAS scale) will be collected for each eye.	██████████

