## 14.2. Sample Size Justification

The plan is to enroll 20 subjects with a target of 15 subjects to complete the study. This is a pilot study and the sample size was not based on any empirical power calculation.

The tables below, provided using the POWER procedure in SAS 9.4, summarizes statistical power based on the following assumptions:

- Testing for superiority with 0 VAS points and equivalence with +/- 10 VAS points
- True difference for superiority: 5, 7.5, 10 points and for equivalence: -5, 0, -5 points
- Estimated standard deviations of 15 and 20 points
- Intraclass correlations of 0.4, 0.6, and 0.8
- Two-sided type I error rate of 0.05
- 15 subjects successfully complete the study

Table 3: Power Analysis for the Primary Hypothesis (Superiority)

Difference (Test-Control)	Estimated Standard Deviation	Intraclass Correlation		
		0.4	0.6	0.8
5.0	15	0.300	0.393	0.617
5.0	20	0.211	0.269	0.425
7.5	15	0.515	0.661	0.897
7.5	20	0.351	0.460	0.705
10.0	15	0.724	0.864	0.987
10.0	20	0.515	0.661	0.897

The study is appropriately powered (power above 80%) to show superiority of anesthetized eyes over eyes that received the placebo when the difference in VAS comfort is at least 7.5 points and the intraclass correlation is at least 0.8.

Table 4: Power Analysis for the Primary Hypothesis (Equivalence)

Difference (Test-Control)	Estimated Standard Deviation	Intraclass Correlation		
		0.4	0.6	0.8
-5.0	15	0.259	0.386	0.617
-5.0	20	0.081	0.202	0.422
0.0	15	0.453	0.728	0.974

Difference (Test-Control)	Estimated Standard Deviation	Intraclass Correlation		
		0.4	0.6	0.8
0.0	20	0.117	0.334	0.794
5.0	15	0.259	0.386	0.617
5.0	20	0.081	0.202	0.422

The study is appropriately powered (power above 80%) to show equivalence between comfort scores at post-treatment and 5-minute post-application when there is no difference (0 VAS points) and the intraclass correlation is at least 0.8.

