### 14.5. Primary Analysis

#### VAS Comfort

VAS Comfort score at 5 and 10 minutes post treatment will be analyzed separately using a linear mixed model. The model will include the following experimental design factors: treatment, sequence of treatment, region, sequence of region, period, time event, and first-order carryover as fixed effects. Baseline characteristics such as age and gender may be included as covariates when appropriate. The covariance between residual errors for the same subject across periods will be modeled using one of the following covariance structures: Compound Symmetry (CS) or Unstructured (UN). The covariance structure that returns the lowest Akaike Information Criteria Corrected (AICC) will be selected as the structure that best fits the data. The Kenward and Roger method will be used for the calculation of denominator degrees of freedom.

The null and alternative hypothesis for superiority of anesthetized eyes compared to eyes that received the placebo with respect to VAS comfort at post treatment, where  $\mu_A - \mu_P$  is the difference in VAS comfort between anesthesia and placebo treatments, is as follows:

$$\begin{aligned}H_0: \mu_A - \mu_P &\leq 0 \\H_A: \mu_A - \mu_P &> 0\end{aligned}$$

The hypothesis will be tested via corresponding two-sided 95% confidence interval for least-squares mean difference (anesthesia minus placebo) of VAS comfort. Superiority will be concluded if the lower limit is greater than 0 for at least one of the three ocular regions (upper lid margin, lower lid margin, or cornea).

The null and alternative hypothesis for equivalence of VAS comfort scores at post-treatment and 5-minutes post-application, where  $\mu_1 - \mu_2$  is the difference in VAS comfort score between post-treatment and 5-minutes post-application, is as follows:

$$\begin{aligned}H_0: |\mu_1 - \mu_2| &\geq 10 \\H_A: |\mu_1 - \mu_2| &< 10\end{aligned}$$

The hypothesis will be tested via corresponding two-sided 95% confidence interval for least-squares mean difference (post treatment minus post application) in VAS comfort score. Equivalence will be concluded if the upper limit is less than 10 and the lower limit is greater than  $-10$ .

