### VAS Comfort (Change)

VAS Comfort score change from pre-treatment to 5 and 10 minute post-treatment values will be analyzed separately using a linear mixed model. The model will include the following experimental design factors: treatment, sequence of treatment, region, sequence of region, period, and first-order carryover as fixed effects; subject as a random effect. Baseline characteristics such as age and gender may be included as covariates when appropriate. The covariance between residual errors for the same subject across periods will be modeled using one of the following covariance structures: Compound Symmetry (CS) or Unstructured (UN). The covariance structure that returns the lowest Akaike Information Criteria Corrected (AICC) will be selected as the structure that best fits the data. The Kenward and Roger method will be used for the calculation of denominator degrees of freedom.

The null and alternative hypothesis for superiority of anesthetized eyes compared to eyes that received the placebo with respect to VAS comfort change from pre-treatment, where  $\Delta_A - \Delta_P$  is the difference in VAS comfort change from pre-treatment between anesthesia and placebo treatments, is as follows:

$$\begin{aligned}H_0: \Delta_A - \Delta_P &\leq 0 \\H_A: \Delta_A - \Delta_P &> 0\end{aligned}$$

The hypothesis will be tested via corresponding two-sided 95% confidence interval for least-squares mean difference (anesthesia minus placebo) of VAS comfort change from pre-treatment. Superiority will be concluded if the lower limit is greater than 0 for at least one of the three ocular regions (upper lid margin, lower lid margin, or cornea).

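### The primary models name no same-visit term for the fellow-eye pair, and the raw-score model omits the pre-treatment score; adding both is a cheap but conditional gain in precision

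*Combined protocol and SAP*

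**What the plan says.** **Design.** Section 4.1 has one region of one eye anesthetized "whilst the fellow eye will receive a saline placebo treatment in the same location". Section 5.1 adds: "For each region within a sequence, the two treatments will be randomly assigned to the left and right eye". The treatment contrast is therefore between fellow eyes within a visit.

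**Raw-score model (14.5, VAS Comfort).** The fixed effects include "sequence of region, period, time event, and first-order carryover as fixed effects". On covariance the text reads "The covariance between residual errors for the same subject across periods will be modeled using one of the following covariance structures"; the options are CS and UN, chosen by the lowest AICC. No subject, eye or subject-by-visit effect is named. The 5- and 10-minute scores are to be analysed separately, yet time event is a factor and its levels are not listed. On covariates: "Baseline characteristics such as age and gender may be included as covariates when appropriate".

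**Change model (14.5, VAS Comfort (Change)).** The covariance sentence is the same, and the list of terms ends "first-order carryover as fixed effects; subject as a random effect".

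**Data in hand.** Before treatment at each of Visits 2 to 4 (7.2, step 2.11): "Subjective comfort scores (vertical VAS scale) will be collected for each eye". This score enters a primary analysis only by subtraction, in the change model.

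**Planning.** Section 14.2 assumes "Intraclass correlations of 0.4, 0.6, and 0.8", without separating same-visit from cross-visit correlation. Sections 14.1 and 14.2 describe a feasibility or pilot study whose size was not set by a power calculation.

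**The concern.** When treated and control eyes are rated on the same evening, the natural error term is the within-visit eye difference. Anything that makes the whole evening better or worse for both eyes drops out of it. A covariance described only across periods has no evident place for that. If one common correlation is imposed on same-evening and different-day scores, day-to-day variation leaks into the standard error of the eye contrast.

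The raw-score model also leaves unused an eye-level baseline that the study already collects. The covariates it gives as examples, age and gender, are identical for both eyes of a subject and cannot sharpen a comparison between them.

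At stake is power. The plan draws yes/no superiority conclusions from about 15 completers, where avoidable error variance can hide a real effect.

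**Working it through.** **The plan's own figure.** Table 3 gives 0.515 / 0.661 / 0.897 at 7.5 points, SD 15, ICC 0.4 / 0.6 / 0.8. A paired t-test with n = 15, 14 df and SD of the difference = 15 × √(2(1 − ICC)) = 16.43 / 13.42 / 9.49 reproduces these and all 18 cells to three decimals, at one-sided 0.05. Under the 95% interval rule of 14.5 the same calculation gives 0.377 / 0.522 / 0.812. With uncorrelated eyes (two-sample t) it gives 0.262. So the planning table relies on a pairing that the model text does not write out. All figures below use the 95% interval rule for one region.

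**Inputs.** From 14.2: 7.5 points, SD 15, 15 completers. Assumed, because the documents do not give them: rw (same-visit correlation), rb (cross-visit correlation), and r (correlation between pre- and post-treatment eye differences). The check fits region-by-treatment cell means to complete, balanced data and leaves out period, sequence and carryover.

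**(a) Pairing, six post-treatment scores per subject.** There are 15 × 3 × 2 = 90 scores. Removing 6 cell means and 14 subject df leaves 70 residual df under CS: 42 within visits (45 eye differences less 3 region means) and 28 between visits. The CS residual variance is SD²(1 − r̄), with r̄ the average correlation over all pairs of scores. Each score has one same-visit and four cross-visit partners, so r̄ = (rw + 4rb)/5 and

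SE ratio = √((1 − r̄)/(1 − rw)) = √(1 + 0.8(rw − rb)/(1 − rw)).

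At 0.8/0.6 this is √1.8 = 1.34; at 0.6/0.4 it is √1.4 = 1.18. The true SEs are 9.49/√15 = 2.45 and 13.42/√15 = 3.46. Power is roughly Φ((7.5 − t × fitted SE)/true SE), with t = 1.994 on 70 df and 2.018 on 42 df:

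- 0.8/0.6: CS (7.5 − 1.994 × 3.29)/2.45 = 0.39, power 0.65. Visit term (7.5 − 2.018 × 2.45)/2.45 = 1.04, power 0.85.
- 0.6/0.4: CS (7.5 − 1.994 × 4.10)/3.46 = −0.19, power 0.42. Visit term (7.5 − 2.018 × 3.46)/3.46 = 0.15, power 0.56.

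Simulation (20,000 trials per setting) agrees:

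| rw/rb | Power, CS | Power, visit term | One-sided error, CS |
|---|---|---|---|
| 0.8/0.8 | 0.86 | 0.85 | 2.5% |
| 0.8/0.7 | 0.76 | 0.85 | 0.9% |
| 0.8/0.6 | 0.65 | 0.85 | 0.5% |
| 0.6/0.6 | 0.57 | 0.56 | 2.5% |
| 0.6/0.4 | 0.43 | 0.56 | 1.2% |

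Mean interval width falls from 13.1 to 9.8 points at 0.8/0.6 and from 16.3 to 13.9 at 0.6/0.4.

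*If time event brings the morning scores into the same block (twelve scores).* Then r̄ = (rw + 2m + 8rb)/11, with m the same-visit morning-evening correlation. For m between rb and rw, CS power is 0.63–0.68 at 0.8/0.6 and 0.42–0.44 at 0.6/0.4, much as before. Equal variances matter here: with a morning SD of 10 and all correlations 0.8, the CS standard error is 8% too narrow and one-sided error is 3.7%.

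*UN.* Over six eye-by-visit scores UN would capture the pairing, but it has 21 parameters for 15 subjects. In simulation AICC preferred it to CS in under 4% of trials at 0.8/0.8, 0.8/0.7, 0.8/0.6 and 0.6/0.4 (about 22% at 0.8/0.4). A UN over three periods alone is 3 × 3 and has no slot for two eyes per period.

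*Change scores.* An evening effect shared by the pre- and post-treatment scores cancels on subtraction, so the gain is smaller or nil.

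**(b) Pre-treatment score.** Adjustment multiplies the variance of the eye difference by 1 − r² and costs 1 df. Subtraction multiplies it by 2(1 − r) if the SDs are equal. At r = 0.5 the factors are 0.75 and 1.00. Simulated power in the joint three-region model at ICC 0.6:

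| r | 0 | 0.3 | 0.5 | 0.7 |
|---|---|---|---|---|
| Raw score, no covariate | 0.56 | 0.56 | 0.56 | 0.56 |
| Raw score, covariate (within-visit slope) | 0.55 | 0.59 | 0.67 | 0.83 |
| Planned change score | 0.32 | 0.43 | 0.56 | 0.78 |

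On 15 pairs alone, r = 0 gives 0.49 against 0.52 (ICC 0.6) and 0.78 against 0.81 (ICC 0.8); break-even is near r = 0.3. A single slope without the visit mean mixes between-subject and between-visit relations into the eye contrast. At r = 0, with those correlations assumed 0.8, it gives 0.52 against 0.56 at 0.6/0.4 and 0.79 against 0.85 at 0.8/0.6.

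**The case against.** The best case for the plan is that nothing it concludes would be wrong. The study is a pilot, the loss is on the conservative side when variances are equal, and the gain depends on correlations that nobody has stated. With equal correlations and r = 0, making both changes lowers power slightly, from 0.57 to 0.55 at ICC 0.6. All of that stands and limits the point to a precision improvement.

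Several stronger readings are tempting and should be resisted:

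- *The plan ignores the pairing.* Not established. CS over one subject block does correlate fellow eyes, and UN over six scores would model the pair fully. The text leaves the indexing open.
- *The tests are invalid or biased.* No. Neither gap causes expected bias. The anti-conservative result above needs both the twelve-score layout and unequal variances, which the documents do not state.
- *Random subject in the change model duplicates CS.* It may. If CS is fitted across periods within each eye, it does not.
- *Baseline is neglected.* Change from pre-treatment is a primary hypothesis in its own right (2.3), and the covariate list is open-ended, so a pre-treatment covariate is not barred. It is simply not prespecified.

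The covariate also has a practical weakness. Under steps 2.12 to 2.15 the right eye is treated and then scored at 5 and 10 minutes before the left eye is treated, so the left eye's pre-treatment score is more than 10 minutes old by then. For the cornea, the lens is also removed and reapplied between scores. Both may lower r, by an unknown amount. Against the better of the two planned analyses at ICC 0.6, the covariate changes power by about −1 / +3 / +11 / +5 points at r = 0 / 0.3 / 0.5 / 0.7.

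**Conclusion.** The point holds as a cheap, conditional improvement. The models do not specify a same-visit pairing term. If CS is applied over all of a subject's scores and variances are equal, raw-score power falls by 13 points (0.56 to 0.43 at 0.6/0.4) to 20 points (0.85 to 0.65 at 0.8/0.6), and there is no loss when the two correlations are equal. AICC selection of UN is unlikely to rescue this in the settings examined. The visit term is the firmer part, because it costs about 1 point if unnecessary.

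The pre-treatment covariate is second in order and less certain: roughly 3 points gained at r = 0.3 and 11 at r = 0.5 in the joint model at ICC 0.6, nothing or a small loss near r = 0. All sizes rest on the assumed rw, rb and r, one region, balanced complete data, and a model without period, sequence or carryover terms. Confidence is medium, because the documents state neither the indexing nor the correlations.

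**What to change.** Keep the hypotheses in 2.3 and change the wording of 14.5.

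1. **Main change, both models.** State how the two eyes and the levels of time event are indexed. Specify random subject plus random subject-by-visit effects, or an equivalent covariance for two eyes within a visit, in place of CS or UN across periods. Do not combine a random subject effect with CS over the same subject block.
2. **Second, smaller change, raw-score superiority model only.** Prespecify the same eye's pre-treatment VAS at that visit, together with the visit mean of the two eyes, so that the slope applied to the eye contrast is the within-visit one. Fit the equivalence comparison with the 5-minute post-application score as a separate model without this covariate. Do not add it to the change model too, because hypotheses 1 and 2 would then yield the same treatment estimate.

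**Cost.** SAP text and one extra model fit; no new data, visits or hypotheses. If a term proves unnecessary, the price is about 1 point of power each in a joint model, or 3 to 4 points for the covariate if a region is analysed on its 15 pairs alone.

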## 2.3. Hypotheses

### Primary Hypotheses

1. Post-treatment subjective scores of comfort (VAS scale) for anesthetized eyes are superior to eyes that received the placebo for at least one of the ocular regions (upper lid margin, lower lid margin, or cornea).
2. Comfort change from pre-treatment for anesthetized eyes is superior to eyes that received the placebo for at least one of the ocular regions (upper lid margin, lower lid margin, or cornea).
3. Post-treatment subjective scores of comfort (VAS scale) for anesthetized eyes are equivalent to 5-minute post lens application levels in the morning for at least one of the ocular regions (upper lid margin, lower lid margin, or cornea). An equivalence margin of 10 points will be used.

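### The Section 14.5 equivalence rule drops hypothesis 3's limits to anesthetized eyes and to a region; read literally with the main-effects model listed, it tests an average over both treatments and all regions

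*Combined protocol and SAP*

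**What the plan says.** - Section 2.3, primary hypothesis 3: "Post-treatment subjective scores of comfort (VAS scale) for anesthetized eyes are equivalent to 5-minute post lens application levels in the morning"; the hypothesis is met if any single region qualifies. On the margin: "An equivalence margin of 10 points will be used".
- Section 14.5, VAS Comfort, equivalence: μ1 − μ2 "is the difference in VAS comfort score between post-treatment and 5-minutes post-application, is as follows". The interval is for the "least-squares mean difference (post treatment minus post application) in VAS comfort score". The decision rule reads "Equivalence will be concluded if the upper limit is less than 10 and the lower limit is greater than" −10, and stops there. It names no treatment and no region.
- Section 14.5, VAS Comfort, superiority: the contrast is named as anesthesia minus placebo, and "Superiority will be concluded if the lower limit is greater than 0 for at least one of the three ocular regions".
- Section 14.5, model: "treatment, sequence of treatment, region, sequence of region, period, time event, and first-order carryover as fixed effects". No interaction is listed. The 5- and 10-minute scores are analyzed separately.
- Sections 4.1 and 7.2: at each visit one eye receives anesthetic and the fellow eye receives saline at the same site. The 5-minute morning score (step 2.3) is taken for both eyes, so saline eyes also have a post-treatment minus morning difference.
- Section 14.2 describes the equivalence comparison without naming a treatment or region. Section 14.4 sets an overall type I error rate of 5%.

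**The concern.** The decision rule and the hypothesis it serves do not describe the same quantity. The superiority paragraph of the same section states both limits and the equivalence paragraph states neither. In a model with main effects only, the effect of time event is a single number common to both treatments and all regions. An analyst who programs Section 14.5 as it stands gets that number. One who reads Section 2.3 back into it gets three region-specific contrasts in anesthetized eyes, which need terms that the model does not list.

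The choice can change the answer to a primary hypothesis. If anesthesia restores morning comfort in one region, saline eyes and the other two regions can pull the average out of the margin. If anesthetized and saline eyes move in opposite directions, the average can lie inside the margin although neither group does.

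**Working it through.** **Inputs.** From Section 14.2: 15 completers, margin ±10, SD 15 or 20, intraclass correlation (ICC) 0.4, 0.6 or 0.8. From Section 14.5: two-sided 95% interval. Assumed, because the documents give no values: the shifts from morning; a correlation of 0.5 to 0.8 between fellow eyes' shifts at a visit; and 0.4 between shifts at different visits.

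**1. Reproduce Table 4.** Take one pair of scores per subject. The SD of the difference is σd = SD × √(2(1 − ICC)), with 14 degrees of freedom and power integrated over the distribution of the sample SD. At a true difference of 0, with each one-sided test at 0.05, ICC 0.4/0.6/0.8 gives 0.453/0.728/0.974 (SD 15) and 0.117/0.334/0.794 (SD 20). These equal the table. So Table 4 describes a contrast with one eye and one region per subject.

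**2. The same contrast under the Section 14.5 rule.** A 95% interval puts 0.025 on each side. Power becomes 0.237/0.536/0.933 (SD 15) and 0.032/0.146/0.626 (SD 20). This is the benchmark for the intended test in one region. (That Table 4 matches a 90% rather than a 95% interval is a separate matter.)

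**3. The pooled contrast.** Each completer gives 2 eyes × 3 regions = 6 equally weighted shifts. With fellow-eye correlation r,

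Var(mean of six) = σd² × [6 + 6r + 24 × 0.4] / 36,

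which is 0.517σd² at r = 0.5 and 0.567σd² at r = 0.8. At ICC 0.8, σd = 15 × √0.4 = 9.49 or 20 × √0.4 = 12.65. The standard error over 15 subjects is 1.76 to 1.84 (SD 15) or 2.35 to 2.46 (SD 20).

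**4. Is Table 4 the pooled contrast?** No. At ICC 0.4, true difference 0 and one-sided 0.05, the pooled contrast would have power 0.82 to 0.86 at SD 15 (table: 0.453) and 0.45 to 0.51 at SD 20 (table: 0.117).

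**5. One region restored, the other five cells 10 points below morning.** The pooled mean is −10 × 5/6 = −8.33, only 1.67 inside the margin.

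| ICC | SD | Intended contrast, restored region | Pooled contrast |
|---|---|---|---|
| 0.8 | 15 | 0.933 | 0.13–0.14 |
| 0.8 | 20 | 0.626 | 0.09–0.10 |
| 0.6 | 15 | 0.536 | 0.09 |
| 0.6 | 20 | 0.146 | 0.06–0.07 |
| 0.4 | 15 | 0.237 | 0.07 |
| 0.4 | 20 | 0.032 | 0.04–0.05 |

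With a 15-point decline the pooled mean is −15 × 5/6 = −12.5, outside the margin, and at ICC 0.8 pooled power is under 0.01.

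**6. All three regions restored, saline eyes at the decline (ICC 0.8).** The pooled mean is half the decline. Pooled power over both SDs is 0.47–0.75 at 10 points, 0.16–0.26 at 15 and about 0.025 at 20. The intended contrast stays at 0.933 or 0.626 per region.

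**7. False equivalence (ICC 0.8).** With anesthetized eyes at −10 (on the margin) and saline eyes at −5, the pooled mean is −7.5 and equivalence is declared 16–26% of the time, against 2.5% per region for the intended contrast. With anesthetized eyes at +10 and saline eyes at −10 in every region, the pooled mean is 0 and the figure is 93–99.9%, again against 2.5%.

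**The case against.** The strongest reply is that Section 14.5 never mentions pooling. It is silent, and Section 2.3 of the same document supplies the treatment, region clause and margin. Table 4 is titled as the equivalence power analysis and fits a contrast with one pair per subject, which suggests what was intended. This stands: the documents do not support a claim that the plan prescribes a test over all eyes. It does not close the gap, because Section 14.10 says the analysis follows the sections as written, and the intended contrast cannot be estimated from the listed terms.

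A second reply is that the model also lacks a treatment-by-region term although superiority is judged by region, so the list need not be complete. That is fair, and it means the list alone does not show an intention to pool. But the superiority rule names its contrast and the equivalence rule does not.

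A third is that the document drops qualifiers elsewhere. The secondary equivalence rule in Section 14.6 omits the reference to the cornea. There, however, the lens-removal score exists only on the corneal day, so the region is not in doubt. Nothing comparable settles the primary rule.

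Three further inferences go too far. The fellow eyes are not untreated; they receive saline. The 93–99.9% figure is not an expected error rate: it needs a 20-point treatment difference in all three regions, twice the largest value in Section 14.2 (10 points). And the trial as a whole would not fail on this, since it is a pilot with two other primary hypotheses.

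**Conclusion.** The concern holds as a mismatch between hypothesis 3 and the rule meant to test it. Taken literally, with the main-effects model, the rule averages over anesthetized and saline-treated eyes and over regions. That is a different hypothesis, so the gap is more than missing detail.

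The likelier harm is missed equivalence. At ICC 0.8, with one region restored and all else 10 points below morning, power falls from 0.933 to 0.13–0.14 (SD 15) or from 0.626 to 0.09–0.10 (SD 20). False equivalence is possible if the shifts offset. All of this rests on assumed shifts and correlations. The loss is smaller at lower ICC, where the intended test is itself weak, and it disappears at ICC 0.4 with SD 20. It is also modest at SD 20, ICC 0.8, if all regions recover and the decline is only 10 points (0.47–0.51 against 0.626). The change should be made before the analysis is programmed.

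**What to change.** In Section 14.5:

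1. Define μ1 − μ2 as the post-treatment minus 5-minute post-application mean difference in anesthetized eyes within a given region.
2. Add the treatment-by-region-by-time event interaction, with its lower-order terms, so that the contrast can be estimated.
3. Conclude equivalence if the 95% interval lies within (−10, 10) in any one of the three regions.
4. State how this fits the 5% overall rate in Section 14.4. With 2.5% per test, the bound for equivalence alone is 3 × 2.5% = 7.5% at one time point, and 6 × 2.5% = 15% if success at either 5 or 10 minutes counts.
5. Report the same contrast for saline eyes descriptively.

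Name the same contrast in the Section 14.2 text on equivalence power.

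No new data are needed. The cost is wider intervals per region than for the pooled contrast, and more parameters with 15 subjects. With two time events per model, the treatment, region and time part grows from 1 + 1 + 2 + 1 = 5 parameters to 2 × 3 × 2 = 12. Some power is also lost if multiplicity is controlled.
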